### **5.5 Concomitant Medications/Vaccinations (Allowed & Prohibited)**

Medications or vaccinations specifically prohibited in the exclusion criteria are not allowed during the ongoing trial. The investigator should discuss any questions regarding this with the Medical Monitor. The final decision on any supportive therapy or vaccination rests with the investigator and/or the subject's primary physician.

Listed below are specific restrictions for concomitant therapy or vaccination following each vaccination:

1. Systemic glucocorticoids (a dose  $\geq 20$  mg/day prednisone or equivalent) within one month, or any other cytotoxic or immunosuppressive drug within twelve months;
2. Any investigational drug within twelve months;
3. Any live virus concomitant vaccinations within 42 days
4. Any other (non-live) concomitant vaccinations within 14 days

### **5.6 Rescue Medications & Supportive Care**

No rescue or supportive medications are specified to be used in this trial.

### **5.7 Subject Withdrawal/Discontinuation Criteria**

Subjects may withdraw from the trial at any time for any reason or the subject may be withdrawn from the trial at the discretion of the investigator should any untoward effect occur. If a subject withdraws from the trial, they will no longer receive treatment or be followed at scheduled protocol visits.

A subject must be withdrawn from the trial if:

1. The subject or legal representative (such as parent or legal representative) withdraws consent from the trial.
2. The subject is lost to follow-up

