#### 4.2.3.2 Safety Endpoints

1. Primary endpoints:
  - a. The occurrence of adverse events, in all participants, in all cohorts:
    - i. The occurrence of each solicited local and systemic AE, during a 14-day follow-up period following each vaccination, and fever, arthritis, arthralgia, rash and blisters/vesicular lesions during a 42-day follow-up period following vaccination.
    - ii. The occurrence of any hematological (hemoglobin level, WBC, lymphocyte, neutrophil, eosinophil and platelet count) and biochemical (ALT, AST and creatinine) laboratory abnormality at days 0, 3, 7, 14, and 28 after each vaccination.
    - iii. The occurrence of any unsolicited AE, during a 42-day follow-up period after each vaccination.
  - b. The occurrence of vaccine related SAE through to Day 365.
2. Secondary endpoints:
  - a. Detection of rVSV by PCR in blood, urine, and saliva in all subjects (D3, 7, 14, 28, 42 following each vaccination)
  - b. Detection of rVSV by PCR in through 42 days from skin vesicles, joint fluid, or skin biopsies if specimens are obtained
  - c. The occurrence of any SAE through to Day 365
  - d. Decrease in CD4 T cell-count (i.e.,  $CD4 < 200 \text{ mm}^3$ )
  - e. Increase in HIV viral load (i.e.,  $VL > 50 \text{ c/ml}$  over two consecutive measurements)

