## **5.8 Subject Replacement Strategy**

A subject who discontinues from the trial will not be replaced.

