##### 7.1.4.2 Withdrawal/Discontinuation

Subjects who discontinue/withdraw from completion of all study related procedures should be encouraged to continue to be followed for safety assessment at all remaining study visits.

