#### **7.2 Assessing and Recording Adverse Events**

An adverse event is defined as any untoward medical occurrence in a patient or clinical investigation subject administered a pharmaceutical product and which does not necessarily have to have a causal relationship with this treatment. An adverse event can therefore be any unfavorable and unintended sign (including an abnormal laboratory finding, for example), symptom, or disease temporally associated with the use of a medicinal product or protocol-specified procedure, whether or not considered related to the medicinal product or protocol-specified procedure. Any worsening of a preexisting condition that is temporally associated with the use of the Study product, is also an adverse event.

Changes resulting from normal growth and development that do not vary significantly in frequency or severity from expected levels are not to be considered adverse events. Examples of this may include, but are not limited to, onset of menses or menopause occurring at a physiologically appropriate time.

Study product includes any pharmaceutical product, biological product, device, diagnostic agent or protocol-specified procedure, whether investigational (including active control medication) or marketed (including normal saline placebo), provided by or distributed by the Sponsor for human use in this study.

Adverse events may occur during clinical trials, or as prescribed in clinical practice, from overdose (whether accidental or intentional), from abuse and from withdrawal.

All adverse events that occur after the consent form is signed but before allocation/randomization must be reported by the investigator if they cause the subject to be excluded from the trial, or are the result of a protocol-specified intervention, including but not limited to study procedures. From the time of allocation/randomization through 42 days following each vaccination, all adverse events must be reported by the investigator. Such events will be recorded at each examination on the Adverse Event case report forms/worksheets. The reporting timeframe for adverse events meeting any serious criteria is described in section 7.2.3.1. The investigator will make every attempt to follow all subjects with non-serious adverse events for outcome.

Electronic reporting procedures can be found in the Electronic Data Capture (EDC) data entry guidelines. Paper reporting procedures can be found in the Investigator Trial File Binder (or equivalent).

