#### **7.2.4 Immediate Reporting of Adverse Events to the Sponsor**

##### **7.2.4.1 Serious Adverse Events**

A serious adverse event is any adverse event occurring at any dose or during any use of Study product that:

- results in death;
- is life threatening;
- results in persistent or significant disability/incapacity;
- results in or prolongs an existing inpatient hospitalization;
- is a congenital anomaly/birth defect;
- is another important medical event.

**Note:** In addition to the above criteria, adverse events meeting either of the below criteria, although not serious per ICH definition, are reportable to the Sponsor in the same timeframe as SAEs to meet certain local requirements. Therefore, these events are considered serious by the Sponsor for collection purposes.

- Is a cancer;
- Is associated with an overdose.

Refer to Table 4 for additional details regarding each of the above criteria.

For the time period beginning when the consent form is signed until treatment allocation/randomization, any serious adverse event, or follow up to a serious adverse event, including death due to any cause, that occurs to any subject must be reported within 24 hours to the Sponsor if it causes the subject to be excluded from the trial, or is the result of a protocol-specified intervention or procedure.

For the time period beginning at treatment allocation/randomization through 365 days following first vaccination, any serious adverse event, or follow up to a serious adverse event, including death due to any cause, whether or not related to the Study product, must be reported within 24 hours to the Sponsor either by electronic media or paper. Electronic reporting

procedures can be found in the EDC data entry guidelines. Paper reporting procedures can be found in the Investigator Trial File Binder (or equivalent).

Additionally, any serious adverse event brought to the attention of an investigator who is a qualified physician at any time outside of the time period specified in the previous paragraph also must be reported immediately to the Sponsor if the event is either:

1. A death that occurs prior to the subject completing the trial, but outside the time period specified in the previous paragraph.

or

2. A serious adverse event that is considered by an investigator who is a qualified physician to be vaccine related.

All subjects with serious adverse events must be followed up for outcome.

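### Sections 5.7 and 7.1.4.2 conflict on whether a withdrawn subject keeps attending visits, so visit-based safety data can be lost because of the effect being measured

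*Combined protocol and SAP*

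**What the plan says.** Section 5.7 gives two routes out of the trial. Subjects may leave for any reason, or "the subject may be withdrawn from the trial at the discretion of the investigator should any untoward effect occur". The next sentence reads: "If a subject withdraws from the trial, they will no longer receive treatment or be followed at scheduled protocol visits". The section then lists only two cases in which withdrawal is mandatory: consent is withdrawn, or the subject is lost to follow-up. Section 5.8 adds: "A subject who discontinues from the trial will not be replaced".

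Section 7.1.4.2 says that subjects who discontinue or withdraw from completing the study procedures "should be encouraged to continue to be followed for safety assessment at all remaining study visits".

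The primary safety endpoints in section 4.2.3.2 are:
- solicited events over 14 or 42 days;
- laboratory abnormalities to Day 28 after each vaccination;
- "The occurrence of any unsolicited AE, during a 42-day follow-up period after each vaccination";
- vaccine-related SAEs to Day 365.

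VSV detection, any SAE to Day 365, CD4 decrease and viral load increase are secondary.

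On reporting, section 7.2 requires all adverse events through 42 days after each vaccination. Section 7.2.4.1 requires all SAEs through 365 days after the first vaccination.

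**The concern.** The two sections give sites opposite instructions for the same people. Under 5.7, what ends the visits can be an untoward effect, which is what the safety endpoints are meant to measure. Missing data that arise in this way are informative.

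The loss could also differ by arm. V920 is a live vaccine compared with inert saline. Section 4.3.1.3 expects arthralgia in up to 44% of vaccinees in the first week and arthritis in fewer than 5% in the second to third week. A subject withdrawn for an early reaction would miss the scheduled visits at which a later event, a laboratory change or VSV shedding would be found.

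**Working it through.** **1. The two rules side by side.**

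| Question | Section 5.7 | Section 7.1.4.2 |
|---|---|---|
| Who is covered | A subject who withdraws from the trial; the preceding sentence names both the subject's choice and the investigator's discretion | Subjects who discontinue or withdraw from completing study procedures |
| What happens to visits | Scheduled visits end | Subject is encouraged to attend all remaining visits for safety |
| Force | Stated as fact | Encouragement, not a requirement |

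No text says that the two sections cover different groups. Nothing defines a status of no further vaccination but continued follow-up.

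**2. What survives if 5.7 is followed.**

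- *Protected in part:* events already reported. Section 7.2 says: "The investigator will make every attempt to follow all subjects with non-serious adverse events for outcome". Section 7.2.4.1 says: "All subjects with serious adverse events must be followed up for outcome". The reporting windows are set by date, not by attendance.
- *Weakened:* detection of new events. Section 7.1.2 monitors both non-serious events and SAEs at visits, and section 7.2 has events recorded at each examination.
- *Not protected:* scheduled hematology and chemistry, VSV in blood, urine and saliva, CD4, viral load and serology. These exist only if the visit takes place.

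**3. Whether the analysis plan repairs the loss.** Section 8.2.4.2 keeps every dosed subject in the safety population and refers to section 8.2.5 for missing safety data. Sections 8.2.5.1 to 8.2.5.3 contain no such method. An event that nobody saw could therefore be counted as no event.

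**4. Scale only, not an estimate.** The plan's nearest figure is 80% power for a 12-point difference from a 1% control rate, with 200 V920 and 50 placebo subjects (section 8.2.7). To reproduce it, take 1% against 13%, two-sided 5%:

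- pooled rate = (0.01×50 + 0.13×200)/250 = 26.5/250 = 0.106
- null standard error = √[0.106×0.894×(1/50 + 1/200)] = 0.0487
- alternative standard error = √[0.01×0.99/50 + 0.13×0.87/200] = 0.0276
- z = (0.12 − 1.96×0.0487)/0.0276 ≈ 0.89, so power ≈ 0.81

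The plan's figure is reproduced. Exact power for Fisher's test is 0.83.

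At 13%, 0.13×200 = 26 V920 subjects have the event. The table assumes that some of these events go unseen, that no placebo event does, and that all 200 subjects stay in the denominator.

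| V920 events unseen (assumed) | Observed V920 rate | Fisher power |
|---|---|---|
| 0 | 26/200 = 13.0% | 0.83 |
| 2 | 24/200 = 12.0% | 0.77 |
| 4 | 22/200 = 11.0% | 0.69 |
| 6 | 20/200 = 10.0% | 0.61 |

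The counts of unseen events are assumptions. Nothing in the documents says which row, if any, would apply.

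**The case against.** Several points on the other side have force.

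- **The stopping sentence is in the active voice.** It refers to a subject who withdraws, while investigator withdrawal is described in the passive. That it covers both is the natural reading of adjacent sentences, but it is not spelled out. This stands as a limit on certainty.
- **The sections might describe full and partial withdrawal.** Section 5.7 speaks of the trial and 7.1.4.2 of completing study procedures. The reading is possible, but no text states it, and 7.1.4.2 itself includes those who withdraw.
- **Reporting continues by date.** This is true, and it makes SAEs the best-protected outcome. It does not replace scheduled samples or examinations. The effect that prompts a withdrawal has been seen, so what is exposed is later or new findings.
- **The mechanism is narrow.** Cohorts 1 to 4 (200 of 250 subjects) receive one dose, so there is no later vaccination to stop and less reason to withdraw anyone for a reaction. This stands.

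A reader might go further and infer that a Cohort 5 subject who reacts to dose 1 and misses dose 2 is thereby withdrawn. The documents do not say so. Section 7.1.1.8 handles an interrupted vaccination plan by consultation and a documented decision, and Table 4 records stopping the vaccine as a separate item. The protocol simply gives no follow-up rule for that subject.

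A reader might also apply the 10% dropout figure to calculate a biased SAE rate. That figure is an assumption of the immunogenicity power calculation, not a rate of withdrawal for adverse events. The calculation would also need SAE risks that the documents do not give, and it would drop leavers whom the safety population keeps.

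**Conclusion.** The point holds as a conflict in current text with a real but unquantified consequence. If 5.7 is followed, visit-based safety data can be lost for reasons tied to the outcome: scheduled laboratory tests, VSV, CD4, viral load, and new adverse events found at visits within 42 days of each vaccination. The missing method in section 8.2.5 leaves that loss without an analytic answer.

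The conclusion rests on reading 5.7's stopping sentence as covering investigator withdrawal. That more subjects would be lost on V920 than on saline is an inference from the expected reactogenicity; the documents do not establish it. Nor is every SAE to Day 365 a primary endpoint: only vaccine-related SAEs are. The size cannot be computed without withdrawal rates by arm and reason. The change is worth making because primary safety data are exposed and the correction is cheap.

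**What to change.** Reconcile 5.7 with 7.1.4.2 in three steps:

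1. State in both sections that data collection at the planned safety and serology visits continues, with the subject's agreement, unless consent is withdrawn or the subject is lost to follow-up. These are already the only two mandatory triggers in 5.7.
2. State in 5.7 that not receiving a further vaccination, which is relevant only to Cohort 5, is not in itself withdrawal from follow-up. This takes no position on who should receive dose 2.
3. Put into section 8.2.5 the missing-safety-data method that 8.2.4.2 refers to. Report withdrawals by arm, reason and day of last safety contact, so that any imbalance can be seen.

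The cost is protocol wording and a short addition to the analysis plan. The visits and samples are already scheduled, and the sample size does not change.

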## **5.8 Subject Replacement Strategy**

A subject who discontinues from the trial will not be replaced.

## **5.9 Beginning and End of the Trial**

The overall trial begins when the first subject signs the informed consent form. The subject participation portion of the overall trial ends when the last subject completes the last study-related phone call or visit, discontinues from the trial or is lost to follow-up (i.e., the subject is unable to be contacted by the investigator). For purposes of analysis and reporting, the overall trial ends when the Sponsor receives the last serology assay result or subject data from the last study-related phone call or visit and the database has been cleaned and locked.

## **5.10 Clinical Criteria for Early Trial Termination**

There are no pre-specified criteria for terminating the trial early. The clinical trial may be terminated early if the extent (incidence and/or severity) of emerging effects/clinical endpoints is such that the risk/benefit ratio to the trial population as a whole is unacceptable. In addition, further recruitment in the trial or at (a) particular trial site(s) may be stopped due to insufficient compliance with the protocol, GCP and/or other applicable regulatory requirements, procedure-related problems or the number of discontinuations for administrative reasons is too high.

## 6.0 TRIAL FLOW CHART

### (COHORTS 1- TO 4)

Trial Period:	Screening	Vaccination	Follow-up							
			1	2	3	4	5	6	7	8
Visit Number/Title:	Screening		1	2	3	4	5	6	7	8
Day:	-30 to 0	0	3	7	14	28	42	180	365	
Scheduling Window (Days):	NA	NA	±1	±1	±3	±3	±7	±14	±28	
Administrative Procedures										
Informed Consent	x									
Inclusion/Exclusion Criteria	x	x								
Subject Identification Card	x	x								
Medical History	x	x								
Concomitant Medication Review	x	x	x	x	x	x	x	x	x	
Randomisation/Vaccine Administration		x								
Clinical Procedures/Assessments										
Full Physical Examination	x									
Height	x									
Weight	x									
Vital Signs (heart rate, blood pressure, respiratory rate, oral/tympanic/axillary temperature)	x	x	x	x	x	x	x	x	x	
Post vaccination Monitoring for Hypersensitivity Reactions (30 Minutes)		x								
Non-Serious Adverse Events Monitoring		x	x	x	x	x	x	x		
Serious Adverse Events Monitoring	x	x	x	x	x	x	x	x	x	

Trial Period:	Screening	Vaccination	Follow-up							
			1	2	3	4	5	6	7	8
Visit Number/Title:	Screening		1	2	3	4	5	6	7	8
Day:		-30 to 0	0	3	7	14	28	42	180	365
Scheduling Window (Days):	NA	NA	±1	±1	±3	±3	±7	±14	±28	
Distribute Patient Memory Aid and Review Procedures with Subject		X								
Review Arthralgia/Arthritis, Rash and/or Vesicular Lesion Reporting Requirements with Subject a	X	X	X	X	X	X	X			
Review Memory Aid with Subject			X	X	X	X	X			
Collect Memory Aid from Subject								X		
Laboratory Procedures/Assessments										
Hematology (~4mls)	X	X	X	X	X	X	X			
Urinalysis	X									
Chemistry (~8mls)	X	X	X	X	X	X	X			
Urine Pregnancy Test (if applicable based on subject's age/gender)	X	X								
HIV serology (if not previously documented) (~8mls)	X									
HBsAg (~8mls)	X									
Hepatitis B & C serology (combined with HBsAg)	X									
ZEBOV-specific Serum Antibodies (~20mls-combined with ZEBOV-specific Neutralizing antibodies)		X b				X		X	X	
ZEBOV-specific Neutralizing antibodies (see volume above)		X b				X		X	X	

Trial Period:	Screening	Vaccination	Follow-up							
			1	2	3	4	5	6	7	8
Visit Number/Title:	Screening		1	2	3	4	5	6	7	8
Day:	-30 to 0	0	3	7	14	28	42	180	365	
Scheduling Window (Days):	NA	NA	±1	±1	±3	±3	±7	±14	±28	
VSV (Blood, Urine and Saliva Sample) (~5mls blood)			x	x	x	x	x			
HIV viral load (~8mls)	x	x	x	x	x	x	x	x	x	
CD4/CD8 T Lymphocytes count (~4mls)	x	x	x	x	x	x	x	x	x	
HIV RNA (reservoirs) (~20 mls combined with HIV DNA and HIV TILDA below)		x				x		x	x	
HIV DNA (reservoirs) (see volume above)		x				x		x	x	
HIV TILDA (reservoirs) (see volume above)		x				x		x	x	
*Biobank samples-optional (~35mls)		xb				x		x	x	
Total Blood volumes (*including optional Biobank sample)	~ 40mls	~64mls (*~89mls)	~29mls	~29mls	~29mls	~69mls (*~94mls)	~29mls	~52mls (*~87mls)	~52mls (*~87mls)	
a. Specimens should be obtained for rVSV detection by PCR in through 42 days from skin vesicles, joint fluid, or skin biopsies b. Specimens should be obtained before vaccination										

**(COHORT 5)**

Trial Period:	Screening	Vaccination	Follow-up												
			2	3	4	5	6	7	8	9	10	11	12	13	14
Visit Number/Title:	Screening	1													
Day:	-30 to 0	0	3	7	14	28	42	56	3 day s pos t dose 2	7 day s pos t dose 2	14 day s pos t dose 2	28 day s pos t dose 2	42 day s pos t dose 2	180	365
Scheduling Window (Days):	NA	NA	±1	±1	±3	±3	±7	±3	±1	±1	±3	±3	±7	±14	±28
Administrative Procedures															
Informed Consent	x														
Inclusion/Exclusion Criteria	x	x							x						
Subject Identification Card	x	x													
Medical History	x	x													
Concomitant Medication Review	x	x	x	x	x	x	x	x	x	x	x	x	x	x	x
Randomisation/			x												
Vaccine Administration			x						x						
Clinical Procedures/Assessments															
Full Physical Examination	x			c.											

Trial Period:	Screening	Vaccination	Follow-up													
			2	3	4	5	6	7	8	9	10	11	12	13	14	
Visit Number/Title:	Screening	1														
Day:	-30 to 0	0	3	7	14	28	42	56	3 day s pos t dos e 2	7 day s pos t dos e 2	14 day s pos t dos e 2	28 day s pos t dos e 2	42 day s pos t dos e 2			
Scheduling Window (Days):	NA	NA	±1	±1	±3	±3	±7	±3	±1	±1	±3	±3	±7	±14	±28	
Height	x															
Weight	x															
Vital Signs (heart rate, blood pressure, respiratory rate, oral/tympanic/axillary temperature)	x	x	x	x	x	x	x	x	x	x	x	x	x	x	x	
Post vaccination Monitoring for Hypersensitivity Reactions (30 Minutes)		x						x								
Non-Serious Adverse Events Monitoring		x	x	x	x	x	x	x	x	x	x	x	x			
Serious Adverse Events Monitoring	x	x	x	x	x	x	x	x	x	x	x	x	x	x	x	
Distribute Patient Memory Aid and Review Procedures with Subject		x						x								
Review Arthralgia/Arthritis, Rash and/or Vesicular Lesion Reporting Requirements with Subject a	x	x	x	x	x	x	x	x	x	x	x	x	x			
Review Memory Aid with Subject			x	x	x	x	x	x	x	x	x	x	x			

Trial Period:	Screening	Vaccination	Follow-up												
			2	3	4	5	6	7	8	9	10	11	12	13	14
Visit Number/Title:	Screening	1													
Day:	-30 to 0	0	3	7	14	28	42	56	3 day s pos t dos e 2	7 day s pos t dos e 2	14 day s pos t dos e 2	28 day s pos t dos e 2	42 day s pos t dos e 2		
Scheduling Window (Days):	NA	NA	±1	±1	±3	±3	±7	±3	±1	±1	±3	±3	±7	±14	±28
Collect Memory Aid from Subject								x					x		
Laboratory Procedures/Assessments															
Hematology (~4mls)	x	x	x	x	x	x	x	x	x	x	x	x	x		
Urinalysis	x														
Chemistry (~8mls)	x	x	x	x	x	x	x	x	x	x	x	x	x		
Urine Pregnancy Test (if applicable based on subject's age/gender)	x	x						x							
HIV serology (if not previously documented) (~8mls)	x														
HBsAg (~8mls)	x														
Hepatitis B & C serology (combined with HBsAg)	x														

Trial Period:	Screening	Vaccination	Follow-up												
Visit Number/Title:	Screening	1	2	3	4	5	6	7	8	9	10	11	12	13	14
Day:	-30 to 0	0	3	7	14	28	42	56	3 day s pos t dos e 2	7 day s pos t dos e 2	14 day s pos t dos e 2	28 day s pos t dos e 2	42 day s pos t dos e 2	180	365
Scheduling Window (Days):	NA	NA	±1	±1	±3	±3	±7	±3	±1	±1	±3	±3	±7	±14	±28
ZEBOV-specific Serum Antibodies (~20mls-combined with ZEBOV-specific Neutralizing antibodies)		x b					x		x b			x		x	x
ZEBOV-specific Neutralizing antibodies (see volume above)		x b				x		x b			x		x	x	x
VSV (Blood, Urine and Saliva Sample) (~5mls blood)			x	x	x	x	x	x	x	x	x	x	x		
HIV viral load (~8mls)	x	x	x	x	x	x	x	x	x	x	x	x	x	x	x
CD4/CD8 T Lymphocytes count (~4mls)	x	x	x	x	x	x	x	x	x	x	x	x	x	x	x
Total Blood volumes	~ 40mls	~44mls	~29 mls	~29 mls	~29 mls	~49 mls	~29 mls	~49 mls	~29 mls	~29 mls	~29 mls	~49 mls	~29 mls	~32 mls	~32 mls
a Specimens should be obtained for rVSV detection by PCR in through 42 days from skin vesicles, joint fluid, or skin biopsies															
b Specimens should be obtained before vaccination															

